To evaluate adherence in participants switching to D/C/F/TAF FDC (Immediate Switch Arm)	 Adherence rates by participant self-report using 4-day recall at Weeks 36 and 48
Exploratory	
Exploratory clinical biomarker	
To assess changes in alpha melanocyte-stimulating hormone when switching to D/C/F/TAF FDC (Immediate Switch Arm)	Change from Baseline in alpha melanocyte-stimulating hormone at Week 48
Exploratory PROs	
To assess changes in eating-related concepts (hunger, appetite, cravings, and satiety) for participants switching to D/C/F/TAF FDC (Immediate Switch Arm)	Change from Baseline in the scores on the DAILY EATS at Week 48
To assess changes in concerns about body shape for participants switching to	• Change from Baseline in the scores on the BSQ-8D at Week 48

CONFIDENTIAL – FOIA Exemptions Apply in U.S.

Objectives	Endpoints
D/C/F/TAF FDC (Immediate Switch Arm)	• Change from Baseline in the proportion of participants who have no concern (<19), mild concern (19-25), moderate concern (26-33) or marked concern (>33) with their body shape on the BSQ-8D at Week 48

Abbreviations: AE: adverse event, ARV: antiretroviral, BMI: body mass index, BSQ 8D: body shape questionnaire, D/C/F/TAF FDC: Darunavir/Cobicistat/Emtricitabine/Tenofovir Alafenamide Fixed dose Combination, DBP: diastolic blood pressure, DEXA: dual energy X ray absorptiometry, FDA: Food Drug Administration, FTC: emtricitabine, HAIR: hypertension, age, insulin, resistance, HIV 1 RNA: human immunodeficiency virus type 1 ribonucleic acid, HIV SI: HIV Symptom Index, HOMA IR: homeostatic model assessment of insulin resistance, INI: integrase, NAFLD: non alcoholic fatty liver disease, NASH: Nonalcoholic fatty liver disease, PGIC: patient global impression of change, PR: protease, PROs: patient reported outcomes, RT: reverse transcriptase, SAE: serious adverse event, SBP: systolic blood pressure.

3.3. Consistency of Effect of Baseline to Week 24 (Immediate Switch) versus Week 24 to Week 48 (Delayed Switch)

Additional secondary objectives/endpoints will evaluate the consistency of effect on outcomes from Baseline to Week 24 in the Immediate Switch Arm versus the Week 24 to Week 48 in the Delayed Switch Arm. The endpoints for the Delayed Switch Arm from Week 24 to Week 48 are the same as for the Immediate Switch to Week 24. Comparison will be made descriptively to evaluate the consistence of outcomes between these two arms for each endpoint.

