2.2. Visit Windows

As subjects do not always adhere to the protocol visit schedule, the following rules are applied to assign actual visits to analysis visits. Listed below are the visit windows and the target days for each visit. The reference day is Study Day 1. If a subject has 2 or more actual visits in one visit window, the visit closest to the target day will be used as the protocol visit for that visit window. The other additional visit(s) will not be used in the summaries or analyses, but they can be used for determination of clinically important endpoints. If 2 actual visits are equidistant from the target day within a visit window, the later visit is used.

All assignments will be made in chronological order. Once a visit date is assigned to a visit window, it will no longer be used for a later time point except for the endpoint. Listed below (Table 2) are the analysis time points (week), visit windows and the target days for each visit defined in the protocol during the treatment phase. The time intervals will be used for reporting of metabolic/weight, efficacy, and safety data.

Table 2. Visit Windows

	Immediate Switch Arm - Time	Delayed Switch Arm - Time	
Analysis	Interval	Interval	Target Time
Time Point a	(Day)	(Day)	Point (Day)
Screening	Day-42 - <day 0<="" td="">Day-42 - <day 0<="" td="">-∞	</day>	</day>	Day-42 - <day 0<="" td="">-∞	</day>	-∞
Baseline b	≤Day 1	≤Day 1	1
Week 4	Day 2 – Day 56	Day 2 – Day 56	29
Week 12	Day 57 – Day 126	Day 57 – Day 126	85
Week 24	Day 127 – Day 210	Day 127 – Day 182	169
Week 28	NA	Day 183 – Day 224	197
Week 36	Day 211 – Day 294	Day 225 – Day 294	253
Week 48	Day 295 – Day 378	Day 295 – Day 378	337

^a For subjects discontinuing treatment early, data collected at that visit will count towards the time interval based on days relative to baseline.

Note: Target Time Point (Day)=Week $x\times7 +1$; Time Interval (Day), for example, Start day=127=(85+169)/2 and then obtain the previous interval End day=127-1=126. Similarly, for other intervals' Start day and End day.

Phases will be constructed for each subject as follows for adverse events, concomitant therapies, and for the determination of the worst-case/toxicity/change in the cross-tabulations.

^b The baseline visit (Day 1) cannot proceed until the investigator has received all results of the screening visit and participant eligibility has been confirmed.

Trial phase	Start date	End date

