Screening	Minimum of date of signing the informed consent and date of the screening visit, no early than Day -42	1 day before start of treatment or day 1 of treatment whichever the last before first dose.
Treatment	Date of the first intake (after	For ongoing/completed subjects, in order of priority:
Phase I	randomization)	 For delayed switched arm, use first D/C/F/TAF intake date – 1;
		- For immediate switch arm, use Week 24 visit date; if missing then
		 Projected Week 24 visit date
		Projected Week 24 visit date = first dose date $+ (7 \times 24)$.
		In case of withdrawal before Week 24 visit : Date of last intake +7 days. If the last dose date is missing, use the following date in order of priority:
		- The date of treatment termination + 7 days;
		- The first available follow-up visit date-1 day;
		- The earlier of projected Week 24 visit date +7 and Trial discontinuation date + 7, where projected Week 24 visit date = first dose date + (7×24).
Treatment	Treatment Phase I end date +1	For ongoing/completed subjects, in order of priority:
Phase II	day	- Week 48 visit date + 7; if missing then
		 Projected Week 48 visit date +7, where projected Week 48 visit date = first dose date + (7×48).
		In case of withdrawal after Week 24 visit: Date of last intake +7 days. If the last intake date is missing, use the following date in order of priority:
		- The date of withdrawal + 7 days;
		- The first available follow-up visit date-1 day;
		- The earlier of projected Week 48 visit date +7 and trial discontinuation date + 7, where projected Week 48 visit date = first dose date + (7×48).
*Follow-up	End of the last treatment phase +1 day	Trial termination date for all groups (date of last contact)

⁺¹ day contact)

*30 day follow-up visit required for any subject who has ongoing AE or SAE at the time of his last study visit.

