- Change from Baseline in the proportion of participants who have no concern (<19), mild concern (19-25), moderate concern (26-33) or marked concern (>33) with their body shape on the BSQ-8D at Week 24 and Week 48, respectively.

6.2.1.1. Consistency of Effect of Baseline to Week 24 (Immediate Switch) versus Week 24 to Week 48 (Delayed Switch)

Metabolic:

- Change in absolute body weight from Baseline to Week 24 (Immediate Switch Arm) compared to the change in absolute body weight from Week 24 to Week 48 (Delayed Switch Arm)
- The proportion of participants having a >5% change in body weight from Baseline to Week 24 (Immediate Switch Arm) compared to the proportion of participants having a >5% change in body weight from Week 24 to Week 48 (Delayed Switch Arm)
- The proportion of participants having a >3% change in body weight from Baseline to Week 24 (Immediate Switch Arm) compared to the proportion of participants having a >3% change in body weight from Week 24 to Week 48 (Delayed Switch Arm)
- Change in BMI from Baseline through Week 24 (Immediate Switch Arm) compared to the change in BMI from Week 24 through Week 48 (Delayed Switch Arm)
- Change in BMI categories from Baseline through Week 24 (Immediate Switch Arm) compared to the change in BMI categories from Week 24 through Week 48 (Delayed Switch Arm)
- Percent change in body weight from Baseline to Week 24 (Immediate Switch Arm) compared to the percent change in body weight from Week 24 to Week 48 (Delayed Switch Arm).
- Percent change in Visceral Adipose Tissue from Baseline to Week 24 (Immediate Switch Arm) compared to the percent change in Visceral Adipose Tissue from Week 24 to Week 48 (Delayed Switch Arm).
- Change in body composition as measured by DEXA from Baseline through Week 24 (Immediate Switch Arm) compared to the change in body composition from Week 24 through Week 48 (Delayed Switch Arm)
- Change in waist circumference from Baseline to Week 24 (Immediate Switch Arm) compared to the change in waist circumference from Week 24 to Week 48 (Delayed Switch Arm)
- The proportion of participants having a waist circumference of > 40 inches for men and > 35 inches for women at Week 24 (Immediate Switch Arm) compared to the proportion of participants having waist circumference of > 40 inches for men and > 35 inches for women at Week 48 (Delayed Switch Arm)

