- Change in SBP and DBP from Baseline to Week 24 (Immediate Switch Arm) compared to the change in SBP and DBP from Week 24 to Week 48 (Delayed Switch Arm)
- Change in fasting lipids from Baseline to Week 24 (Immediate Switch Arm) compared to the change in fasting lipids from Week 24 to Week 48 (Delayed Switch Arm)
- Change in fasting glucose from Baseline to Week 24 (Immediate Switch Arm) compared to the change in fasting glucose from Week 24 to Week 48 (Delayed Switch Arm)

- Change in in HOMA-IR from Baseline to Week 24 (Immediate Switch Arm) compared to the change in HOMA-IR from Week 24 to Week 48 (Delayed Switch Arm)
- Change in HbA1c from Baseline to Week 24 (Immediate Switch Arm) compared to the change in HbA1c from Week 24 to Week 48 (Delayed Switch Arm)
- Change in leptin and adiponectin from Baseline to Week 24 (Immediate Switch Arm) compared to the change in leptin and adiponectin from Week 24 to Week 48 (Delayed Switch Arm)
- Change in the proportion of participants from Baseline to Week 24 with advanced fibrosis according to the NAFLD fibrosis score (F0-F1, Indeterminate, and F3-F4) (Immediate Switch Arm) compared to the change in the proportion of participants from Week 24 to Week 48 with advanced fibrosis according to the NAFLD fibrosis score (Delayed Switch Arm)
- Change in the proportion of participants from Baseline to Week 24 at high risk of NASH according to the HAIR score (<2 and ≥2) (Immediate Switch Arm) compared to the change in the proportion of participants from Week 24 to Week 48 at high risk of NASH according to the HAIR score (Delayed Switch Arm)
- Proportion of participants having a dose-reduction or complete withdrawal of anti-hypertensive, anti-hyperglycemic, or lipid lowering agents from Baseline to Week 24 (Immediate Switch Arm) compared to Week 24 to Week 48 (Delayed Switch Arm)
- Proportion of participants starting an anti- hypertensive, anti-hyperglycemic, or lipid lowering agent from Baseline to Week 24 (Immediate Switch Arm) compared to Weeks 24 to Week 48 (Delayed Switch Arm)

Safety:

- Incidence of any Grade AEs (related and not related) through Week 24 (Immediate Switch Arm) compared to the incidence of any grade AEs (related and not related) through Week 48 (Delayed Switch Arm)
- Incidence of Grade 3 and 4 AEs (related and not related) through Week 24 (Immediate Switch Arm) compared to the incidence of Grade 3 and 4 AEs (related and not related) through Week 48 (Delayed Switch Arm)

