- Incidence of discontinuations due to AEs through Week 24 (Immediate Switch Arm) compared to discontinuations due to AEs through Week 48 (Delayed Switch Arm)
- Incidence of SAEs (related and not related) through Week 24 (Immediate Switch Arm) compared to Incidence of SAEs (related and not related) through Week 48 (Delayed Switch Arm)
- Change in clinical laboratory tests over time (Baseline to Week 24 for Immediate Switch Arm) compared to the change in clinical laboratory tests over time (Week 24 to Week 48 (Delayed Switch Arm)
- Incidence of Grade 3 and 4 laboratory abnormalities through Week 24 (Immediate Switch Arm) compared to Grade 3 and 4 laboratory abnormalities through Week 48 (Delayed Switch Arm)

Efficacy:

• The proportion of participants with confirmed virologic rebound at Week 24 (Immediate Switch Arm) compared to the proportion of participants with confirmed virologic rebound from Week 24 to Week 48 (Delayed Switch Arm)

- The proportion of participants with virologic response (HIV-1 RNA<50 copies/mL) at Week 24 according to the FDA snapshot algorithm (Immediate Switch Arm) compared to the proportion of participants with virologic response (HIV-1 RNA<50 copies/mL) at Week 48 according to the FDA snapshot algorithm (Delayed Switch Arm)
- The proportion of participants with virologic failure (HIV-1 RNA ≥50 copies/mL) at Week 24 according to the FDA snapshot algorithm (Immediate Switch Arm) compared to the proportion of participants with virologic failure (HIV-1 RNA ≥50 copies/mL) at Week 48 according to the FDA snapshot algorithm (Delayed Switch Arm)
- The proportion of participants having virologic response (HIV-1 RNA<200 copies/mL) at Week 24 according to the FDA snapshot algorithm (Immediate Switch Arm) compared to the proportion of participants having virologic response (HIV-1 RNA<200 copies/mL) at Week 48 according to the FDA snapshot algorithm (Delayed Switch Arm)
- The proportion of participants having virologic failure (HIV-1 RNA ≥200 copies/mL) at Week 24 according to the FDA snapshot algorithm (Immediate Switch Arm) compared to the proportion of participants having virologic failure (HIV-1 RNA ≥200 copies/mL) at Week 48 according to the FDA snapshot algorithm (Delayed Switch Arm)
- Change in CD4+ cell count from Baseline to Week 24 (Immediate Switch Arm) compared to the change in CD4+ cell count from Week 24 to Week 48 (Delayed Switch Arm)

Resistance:

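### Five of the six consistency-of-effect safety endpoints in SAP 6.2.1.1 are worded as 24 weeks (Immediate) against events through Week 48 (Delayed), contradicting the section heading and Protocol 3.3

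*SAP*

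**What the plan says.** The heading of SAP 6.2.1.1 sets the windows for everything under it: "Consistency of Effect of Baseline to Week 24 (Immediate Switch) versus Week 24 to Week 48 (Delayed Switch"). Protocol 3.3 gives the same rule: "The endpoints for the Delayed Switch Arm from Week 24 to Week 48 are the same as for the Immediate Switch to Week 24". It adds that the comparison is descriptive.

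The safety list in SAP 6.2.1.1 has six bullets. Five of them (any-grade AEs, Grade 3 and 4 AEs, discontinuations due to AEs, SAEs, Grade 3 and 4 laboratory abnormalities) give the Delayed arm an end point of Week 48 and no start. The any-grade bullet takes incidence "through Week 24 (Immediate Switch Arm) compared to the incidence of any grade AEs (related and not related) through Week 48 (Delayed Switch Arm"). The discontinuation bullet reads: "Incidence of discontinuations due to AEs through Week 24 (Immediate Switch Arm) compared to discontinuations due to AEs through Week 48 (Delayed Switch Arm"). The sixth, laboratory change, has the intended window: "compared to the change in clinical laboratory tests over time (Week 24 to Week 48 (Delayed Switch Arm").

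SAP 2.2 already defines the periods needed. It says: "Phases will be constructed for each subject as follows for adverse events, concomitant therapies, and for the determination of the worst-case/toxicity/change in the cross-tabulations". For the end of Treatment Phase I the rule begins "For delayed switched arm, use first D/C/F/TAF intake date" and subtracts one day; Treatment Phase II starts the day after Phase I ends.

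SAP 7.1.2 summarises AEs by treatment group and does not mention phase. SAP 4.6, by contrast, tabulates the listed groups of prior and concomitant drugs by treatment group and phase.

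**The concern.** Delayed-arm participants spend the first 24 weeks on their INI + TAF/FTC regimen and only then switch. A Delayed-arm count that runs from Baseline to Week 48 covers two regimens and twice the follow-up of the Immediate-arm count beside it. Safety of D/C/F/TAF that was truly the same in both arms would then look inconsistent, with the later switch appearing worse.

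The discontinuation bullet shows the problem most plainly. Read literally, a Delayed participant who stopped the INI regimen for an AE at Week 10 and never took D/C/F/TAF would count as an event in a comparison meant to describe D/C/F/TAF. The purpose of the trial is the safety and tolerability of switching, so these tables are likely to be read closely even though nothing in them is tested.

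**Working it through.** The plan states no figure for this comparison, so there is none to reproduce. The check has two parts.

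**1. The wording, side by side**

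| Place | Delayed-arm window |
|---|---|
| Protocol 3.3 | Week 24 to Week 48 |
| SAP 6.2.1.1, heading | Week 24 to Week 48 |
| SAP 6.2.1.1, virologic rebound; starting a concomitant agent; laboratory change | Week 24 to Week 48 |
| SAP 6.2.1.1, BMI and body composition | Week 24 named as the start, Week 48 as the end |
| SAP 6.2.1.1, five safety bullets | End at Week 48, no start given |
| SAP 6.2.1, the same AE endpoints | Through Week 24 and through Week 48, as counts from Baseline |

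The last row matters because the main endpoint list uses the same 'through' phrasing for cumulative counts. A programmer who carries that usage into 6.2.1.1 gets 48 weeks against 24, a ratio of 2 to 1, with half the Delayed period on INI + TAF/FTC.

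The treatment-emergent definition does not remove INI-period events. Protocol Section 2 defines study intervention to include the INI + TAF/FTC regimen. Protocol 9.4.4 counts as treatment-emergent any AE from the first administration of study intervention to last dose plus 7 days; SAP 7.1.2 uses the same window for study drug.

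**2. Size if the bullets are followed literally**

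Assumptions, none of them from the documents:
- p is the risk of at least one event in 24 weeks on D/C/F/TAF, the same in both arms.
- r × p is the risk in the 24-week INI period.
- The two periods are independent and there is no dropout.

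Immediate figure: p. Delayed figure: 1 − (1 − p)(1 − r × p).

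| p | r = 0.25 | r = 1 |
|---|---|---|
| 3% | 1 − 0.97 × 0.9925 = 3.7% | 1 − 0.97² = 5.9% |
| 30% | 1 − 0.70 × 0.925 = 35.3% | 1 − 0.70² = 51% |
| 50% | 1 − 0.50 × 0.875 = 56.2% | 1 − 0.50² = 75% |

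The true difference is zero in every cell. If r = 0 the excess vanishes; for any r above zero the Delayed figure is too high. Positive dependence between periods within a participant would make the excess smaller than shown.

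With the Delayed window starting at first D/C/F/TAF intake, both arms contribute about 24 weeks on the same drug and this source of excess is removed. One small asymmetry stays: SAP 2.2 ends Phase II 7 days after the Week 48 visit but ends Immediate-arm Phase I on the Week 24 visit date.

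**The case against.** A reader might infer that INI-period events will be counted and attributed to D/C/F/TAF. The documents do not support that. The heading above the bullets and Protocol 3.3 both give Week 24 to Week 48. SAP 2.2 builds phases for AEs and closes Delayed-arm Phase I the day before the first D/C/F/TAF dose. SAP 2.4.2 assesses safety by the intervention actually received. The bullets can be read as shorthand under their heading, and on that reading the excess is zero. The table specifications sit in a separate document that is not available here, so the programmed window cannot be known.

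A second objection concerns size. Equal risk in both periods is unlikely, since Delayed participants enter on a regimen already stable for at least 6 months. Protocol 4.2 reports that in the earlier switch study 543 of 625 AEs (87%) and 10 of 11 AE discontinuations on D/C/F/TAF fell in the first 24 weeks. That favours the lower end of the range or below it: 82 later events against 543 is a ratio of 0.15, although these are event counts and not participant risks.

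Both objections stand as limits on the consequence. Neither repairs the wording. The heading and the phases show intent, but no sentence ties the consistency AE tables to Phase II, and SAP 7.1.2 is silent on phase where SAP 4.6 is explicit. The heading also leaves the denominator open. SAP 1.3 makes the Week 24 switch optional for Delayed participants, and some may stop before it.

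**Conclusion.** Wrong as written. Five of the six safety bullets state an endpoint that contradicts their own heading and Protocol 3.3. Laboratory change is correctly worded, so the point does not extend to the whole safety list.

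The consequence is conditional. If the bullets are programmed as they stand, the Delayed figure would be inflated whenever the INI-period risk is above zero: on assumed risks, 50% would show as about 56% to 75%, and 3% as about 3.7% to 5.9%. These figures illustrate a range from a quarter of the D/C/F/TAF risk to equal risk, under independence. They are not estimates, because the documents give no AE incidence for this population.

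The comparison is secondary and descriptive, and AEs are not formally tested. The primary endpoint, alpha and the randomised Week 24 safety comparison are unaffected. The change should still be made, because this is a stated endpoint rule that produces a mixed-regimen comparison if followed.

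**What to change.** - In the five bullets of SAP 6.2.1.1, replace 'through Week 48 (Delayed Switch Arm)' with: from first D/C/F/TAF intake to Week 48 (Treatment Phase II), Delayed Switch Arm.
- State the denominator for these Delayed-arm figures: participants who took at least one dose of D/C/F/TAF.
- In SAP 7.1.2 and 7.2.2, state that the consistency AE and laboratory-abnormality tables compare Treatment Phase I (Immediate) with Treatment Phase II (Delayed).

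The cost is a few lines of SAP text and a check that the table specifications agree. The phases are already defined in SAP 2.2, so no new data or derivations are needed.

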For the most comprehensive non-clinical and clinical information regarding D/C/F/TAF FDC, refer to the Investigators Brochure.¹⁹ For further information on the INI + TAF/FTC ARV regimens, please refer to ARV-specific Prescribing Information.

The term "study intervention" throughout the protocol, refers to D/C/F/TAF FDC and INI + TAF/FTC ARV regimen; otherwise, the individual study intervention names are used.

The term "sponsor" used throughout this document refers to the entities listed in the Contact Information page(s), which will be provided as a separate document.

The term "participant" throughout the protocol refers to the common term "subject".

25

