- Screening (approximately 30 days [up to a maximum of 6 weeks])
- Open-Label Treatment (48 weeks)
- Follow-up (for any participant who has an ongoing AE or SAE at the time of his/her last study visit).

Screening Phase

The informed consent form (ICF) must be signed before any study-specific procedures at the start of the Screening Phase. After obtaining the ICF from the participant, selection criteria will be reviewed to confirm the participant's eligibility. At baseline (Day 1), participants who meet all eligibility criteria will be randomized in a 1:1 ratio to one of the following two treatment arms. Randomization will be stratified by sex (Male or Female) and race (Black/African American or Non-Black/African American) at Baseline. All enrolled participants will be assigned randomized treatments in an open-label manner.

- **D/C/F/TAF FDC Arm (Immediate Switch):** Switch to a regimen of DRV 800 mg + COBI 150 mg + FTC 200 mg + TAF 10 mg FDC once daily, (n=55) for 48 weeks;
- Active-Control Arm (Delayed Switch): Continue current INI + TAF/FTC ARV regimen, (n=55) for 24 weeks. After 24 weeks participants will switch to a regimen of DRV 800 mg + COBI 150 mg + FTC 200 mg + TAF 10 mg FDC once daily for an additional 24 weeks.

Treatment Phase

Participants randomized to the Immediate Switch Arm must start D/C/F/TAF FDC within 24 hours of the Baseline visit and will continue to receive D/C/F/TAF treatment for a total of 48 weeks.

Participants randomized to the Delayed Switch Arm will continue their current INI + TAF/FTC ARV regimen for 24 weeks. After Week 24, all participants in the Delayed Switch Arm will be given the option to receive the D/C/F/TAF tablet and will be followed for an additional 24 weeks.

- D/C/F/TAF FDC Arm (Immediate Switch): Switch to a regimen of DRV 800 mg + COBI 150 mg + FTC 200 mg + TAF 10 mg FDC once daily, (n=55) for 48 weeks;
- Active-Control Arm (Delayed Switch): Continue current INI + TAF/FTC ARV regimen, (n=55) for 24 weeks. After 24 weeks participants will switch to a regimen of DRV 800 mg + COBI 150 mg + FTC 200 mg + TAF 10 mg FDC once daily for an additional 24 weeks.

Participants will return for study visits at Weeks 4, 12, 24, 36, and 48. Additionally, participants randomized to the Delayed Switch Arm will have an additional study visit at Week 28 (i.e., 4 weeks after switching from the INI + TAF/FTC ARV regimen to D/C/F/TAF FDC).

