1.4. Statistical Hypotheses for Trial Objectives

The primary goal of this study is to assess the percent change in body weight at Week 24 from Baseline of D/C/F/TAF FDC (Immediate Switch arm) in HIV-1 infected participant who are virologically-suppressed (HIV-1 RNA <50 copies/mL) and have experienced rapid and significant body weight gain in combination with an INI + TAF/FTC ARV regimen (Delayed Switch arm). The statistical hypothesis is the following:

 H_0 : Dt-Dc=0 versus H_1 : Dt-Dc \neq 0.

Where H_0 is the null hypothesis, H_1 is the alternative hypothesis; Dt= percent change in body weight at Week 24 from baseline for treatment D/C/F/TAF (Immediate Switch arm), Dc for the Delayed Switch arm.

The statistical hypothesis will be tested using repeated measures longitudinal method (linear mixed- effects (LME) model) at 0.05 significance level, 2-sided.

For all participants who receive at least 1 dose of study intervention, the descriptive statistics will be provided. Participant information will be analyzed based on the Intent-to-treat (ITT) population, unless otherwise specified.

Primary Endpoint Analyses: Percent change in body weight at Week 24 from Baseline. The primary endpoint analyses will be based on the ITT population. It will be evaluated using LME model with participant as random effect adjusted by baseline BMI and stratification factors (sex and race) in a longitudinal data with repeated measures (percent change in body weight measured at multiple visits).

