2.4.1.1. Intent-to-Treat Analysis Set

The intent-to-treat (ITT) analysis set will include all the subjects who were randomized and received at least 1 dose of treatment subsequent to randomization in the study. Subjects will be grouped according to the treatment arm (D/C/F/TAF FDC or Active-Control) to which they were randomized.

The ITT analysis set is the primary analysis set for primary endpoint (percent change in body weight) analysis. The ITT analysis set is also used for efficacy analysis. Efficacy data up to the last dose date of the randomized study treatment will be included.

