Virologic failure leading to discontinuation will be determined by a medical assessment of the comment fields and other specification reasons for discontinuation to determine if anyone discontinued the trial due to lack of efficacy reasons. Upon further clinical evaluation additional comments or other specification reasons might need to be added, and these will be documented in the DPS. An identified subject will be classified to the snapshot categories as follows:

- Data within window: If an identified subject has HIV RNA data within the window, the HIV RNA data will be used to classify the subject as either at or above the threshold or below the threshold.
- No data within window: If an identified subject does not have HIV RNA data in window, then
 regardless of the last HIV RNA value the subject will be classified as "Virologic failure leading to
 discontinuation".

Virologic response will then be categorized as follows: Yes (virologic response), or No (virologic failure and no viral load data in the Week 24 visit window and Week 48 visit window).

The snapshot approach will also be displayed over time by analysis time points and will follow the same logic as defined above weeks 24 and 48 time point. (Please see Section 2.2. Visit Windows for visit intervals).

Subjects will also be classified as confirmed virologic rebounds if they meet the criteria below:

• Two consecutive HIV RNA ≥200 copies/mL at a scheduled or unscheduled visit after maintaining HIV-1 RNA <50 copies/mL).

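### The virologic consistency comparison names no denominator for the Delayed arm's Week 48 snapshot, so by default it counts participants who left on their INI regimen and never took D/C/F/TAF

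*SAP*

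**What the plan says.** **The aim.** Protocol 3.3 states it as "consistency of effect on outcomes from Baseline to Week 24 in the Immediate Switch Arm versus the Week 24 to Week 48 in the Delayed" group, to be judged descriptively. SAP 1.1.2.3 frames the virologic part as a comparison with people who switch to D/C/F/TAF after 24 weeks on INI + TAF/FTC.

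**The endpoints.** SAP 6.2.1.1 lists four snapshot proportions: response and failure, each at the 50 and 200 copies/mL thresholds. For response at 50, the Immediate arm's Week 24 figure is "compared to the proportion of participants with virologic response (HIV-1 RNA<50 copies/mL) at Week 48 according to the FDA snapshot algorithm (Delayed Switch Arm"). All four follow this pattern. None is restricted to participants who switched. The rebound and post-baseline resistance lines in the same list do limit the Delayed arm to Week 24 to Week 48.

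**The denominator.** SAP 6.2.1.1 names no analysis set. SAP 2.4.1.1 says "The ITT analysis set is also used for efficacy analysis", and SAP 1.4 gives the default: "Participant information will be analyzed based on the Intent-to-treat (ITT) population, unless otherwise specified". ITT requires that a randomised subject "received at least 1 dose of treatment subsequent to randomization in the study". Protocol section 2 says that the term study intervention "refers to D/C/F/TAF FDC and INI + TAF/FTC ARV regimen". SAP 2.4 defines no set that begins at the delayed switch.

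**The classification.** SAP 6.1.2 reduces snapshot to yes or no, with "No (virologic failure and no viral load data in the Week 24 visit window and Week 48 visit window").

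**The switch itself.** SAP 1.3 says "all participants in the Delayed Switch Arm will be given the option to receive the D/C/F/TAF tablet". Protocol 4.1 and SAP 2.1 say that these participants receive D/C/F/TAF after Week 24, without mentioning a choice.

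**The concern.** The objective concerns what happens on D/C/F/TAF. The endpoint describes everyone randomised to the Delayed arm, whether or not they reached D/C/F/TAF. The Immediate figure carries 24 weeks of attrition, all on D/C/F/TAF. The Delayed figure carries 48 weeks, the first 24 of them on INI.

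If the drug did equally well in both settings, the table would still tend to show lower response after the delayed switch. SAP 6.2.2.2 attaches 95% confidence intervals to these proportions, which gives the artefact a formal look. A reader could take it as evidence that delaying the switch worsens virologic outcome.

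**Working it through.** **Plan's own figure.** SAP 1.5: 16/ES² = 16/0.54² = 54.9, so 55 per arm. This reproduces, and N = 55 is used below. The maximum total of 150 would give 75 per arm.

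**Who is in the denominator.** A Delayed participant who takes INI + TAF/FTC after randomisation and leaves at, say, Week 16 has had a dose of study intervention and is in ITT. SAP 2.4.1.1 also limits efficacy data to the last dose of randomised treatment, but that removes data, not people. Treatment Phase II in SAP 2.2 does start at the delayed switch. However, those phases are built for adverse events, concomitant therapies and worst-case cross-tabulations, not for snapshot.

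**How SAP 6.1.2 classifies such a leaver at Week 48:**

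- Left for AE or death: no viral load data, so not a responder.
- Left for another reason, last RNA below threshold or missing: no viral load data, so not a responder.
- Left for another reason, last RNA at or above threshold: virologic failure.
- Left for virologic failure, no RNA in the window: virologic failure.

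**Size for response.** Inputs:

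- N = 55 (SAP 1.5).
- p = 94.9% response among switchers. This is an assumption, borrowed from the Week 48 result of the suppressed-switch Phase 3 study in Protocol 2.2.
- k = Delayed participants who leave before their first D/C/F/TAF dose. The documents give no value, so a range is shown.

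Expected ITT response = p(N − k)/N. Shortfall = pk/N. Per leaver: 0.949/55 = 1.7 points.

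| k | ITT response | Among switchers | Shortfall (points) |
|---|---|---|---|
| 1 | 93.2% | 94.9% | 1.7 |
| 2 | 91.4% | 94.9% | 3.5 |
| 3 | 89.7% | 94.9% | 5.2 |
| 5 | 86.3% | 94.9% | 8.6 |

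In whole numbers with k = 5 and Clopper-Pearson intervals (the SAP's method): 47/55 = 85.5% (73.3 to 93.5) on ITT, against 47/50 = 94.0% (83.5 to 98.7) among switchers. With N = 75 and k = 5 the shortfall is 0.949 × 5/75 = 6.3 points.

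**Failure.** Suppose one true failure on D/C/F/TAF and five leavers, two of whom meet a failure rule while on INI. ITT gives 3/55 = 5.5%; switchers give 1/50 = 2.0%.

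**Opposite direction.** A participant who stays on INI and is suppressed at Week 48 counts as a responder. Against p = 94.9%, each one raises the Delayed figure by (1 − 0.949)/55 = 0.09 points. This is small, but it is still an INI outcome reported as a D/C/F/TAF one.

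**Rebound.** The event window is already Weeks 24 to 48, so leavers only dilute the rate. With one rebound and k = 5: 1/55 = 1.8% against 1/50 = 2.0%.

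**The case against.** The strongest reply is that ITT is inferred, since SAP 6.2.1.1 names no set and the objective in SAP 1.1.2.3 speaks of participants who switch. That is fair as a description of intent. But a programmer following the SAP has only the efficacy set and the default rule, both ITT, and no switched set to select.

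Second, the SAP gives other views. SAP 6.1.2 also defines an observed-data approach that drops missing values, and it presents snapshot subcategories. SAP 4.2 tabulates discontinuation reasons by arm with a Kaplan-Meier graph. These partly expose the artefact. They do not remove it, because the four endpoints name the snapshot algorithm. They do rule out one tempting inference, that the virologic consistency question cannot be answered at all.

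Third, dropout may be low. Suppose all non-response in the suppressed-switch study (94.9% and 93.7% response) is put down to dropout spread evenly over two 24-week periods. Then d = 1 − √0.949 = 2.6% or 1 − √0.937 = 3.2%, which is 1.4 to 1.8 of 55 people. With full suppression otherwise, the gap d(1 − d) is 2.5 to 3.1 points. A reader might instead assume 10% or 15% per period and infer gaps of 9 or 12.8 points. The documents support no such rate.

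Fourth, a switched-only group has stayed 24 weeks on study while the Immediate arm is unselected, which may favour the Delayed arm. This stands, and it is why the ITT result should be kept alongside.

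**Conclusion.** The concern holds. As written, the four Delayed-arm snapshot proportions mix INI-period attrition into a D/C/F/TAF result and do not match the stated objective. The cost is about 1.7 points of response per pre-switch leaver, or 1.7 to 8.6 points for 1 to 5 leavers. That assumes N = 55 and 94.9% response among switchers; the number of leavers is unknown. If nobody leaves or declines before the switch, the problem disappears.

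Three stronger readings might be inferred, and the documents do not support them:

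- **Every leaver becomes a virologic failure.** Only those who left for virologic failure, or for another non-AE/death reason with last RNA at or above the threshold, do so. The rest are no-data non-responders.
- **The bias always runs downwards.** A participant who stayed suppressed on INI biases response upwards.
- **Rebound and resistance events on INI are counted against D/C/F/TAF.** Those lines are already limited to Weeks 24 to 48; only their denominator is open.

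The comparison is secondary, descriptive and not randomised, so the primary endpoint, alpha and power are untouched. It should still be corrected, because following the text as it stands gives a misattributed result.

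**What to change.** - Add to SAP 2.4 a set of Delayed Switch participants with at least one dose of D/C/F/TAF.
- In SAP 6.2.1.1, use it as the Delayed denominator for the four snapshot proportions, counting only discontinuations and viral loads after the first D/C/F/TAF intake.
- Use the same set as the denominator for the rebound and post-baseline resistance proportions.
- Beside these, show the ITT Week 48 result and the number who never switched, with reasons.
- Reconcile the optional-switch wording in SAP 1.3 with Protocol 4.1 and SAP 2.1.

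The cost is SAP wording and one population flag, with no new data. The downside is a slightly smaller, post-randomisation Delayed group selected for staying 24 weeks on study. That is acceptable for a secondary, descriptive, non-randomised comparison, provided that the ITT figure and the never-switched count stay visible.
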